1.5 Protocol Overview

1.5.1 Sample Size

Up to 110 adult subjects age \geq 18 to <70 years old will be enrolled so that approximately 76 subjects complete the entire study at University of Virginia, allowing for up to 31% attrition rate due to the duration of the study protocol).

1.5.2 Protocol Summary

For the proposed studies, the AP system will be deployed with different functionalities at different stages of the trial, resulting in variation in what the subject will be responsible for and what the system will drive. A trial outline is contained in Figure 1 and visits detailed in Figure 5. **Study Phases without the AP system**

CGM Run-in Phase: Study participants will begin with a maximum 2 week run-in period during which they will have a CGM (i.e. sensor-augmented pump therapy or CGM+CSII) but otherwise be on their usual diabetes management with respect to BG monitoring, pump basal rates, insulin-to-carbohydrate ratios and correction factors. This is necessary because some of the study participants will not have had experience with CGMs in the past.

Study Pump Run-in Phase: All subjects will have a run-in period on the study pump of up to two week duration. Subjects who have had prior experience with the study pump may either skip this run-in phase or may require a shorter run-in period depending on their proficiency with the study pump.

Sensor-Augmented Pump (SAP) Therapy: During this phase, the subject is on the study CGM and their personal insulin pump. There are no predictive or control algorithms. The subjects will administer basal and bolus insulin using their usual home insulin parameters.

Study Phases with the AP System

AP system Run-In Phase: Subjects who have not had recent use of the system (more than approximately 2 weeks of use in the past 6 months or more than 2 months of use in the past year) will complete an up to 2-week home use period with the full system in pump only (open loop) configuration where no closed loop algorithms are activated. Subjects who have had prior experience with the system as defined above will not be required to do Visit 5.

USS+SAP (d): USS Virginia plus SAP during the day (d). Subjects will be using the study pump and CGM with the AP system in Pump mode (open loop only, no closed loop algorithms running). The subject will activate the USS Virginia Closed-Loop Control as early as pre-dinner but is expected to activate CLC by bedtime. The subject will continue in Closed-Loop Control until the time of awakening in the morning. The USS will monitor CGM and insulin-on-board data and predicts the patient's risk of hypoglycemia and adjust insulin delivery accordingly.

USS+CLC (d): USS Virginia and Closed Loop Control over 24 hours. This arm will test fullyintegrated closed-loop control (CLC) system. When hypoglycemia is predicted, the USS reduces basal rate insulin to prevent hypoglycemia, or issues an alert that signals that carbohydrates are required to treat hypoglycemia. The USS also generates alerts about correction bolus requests that are considered potentially dangerous, or meal bolus requests that require user approval prior to delivery.

Chapter 2 SUBJECT ENROLLMENT AND STUDY INITIATION

2.1 Study Population

We anticipate recruiting up to 110 subjects, ages ≥18 and <70 years. An equal number of males and females will be recruited, and all racial/ethnic groups will be eligible for participation. Based on our experience, we expect that approximately 76% in each arm will complete the study (N=64) and has been increased to account for inclusion of new devices. The randomization will aim to balance the age/gender distributions of the participants in the two groups and to match the groups by baseline HbA1c.

2.2 Eligibility and Exclusion Criteria

2.2.1 Eligibility

To be eligible for the study, a subject must meet the following criteria at time of screening:

- Clinical diagnosis, based on investigator assessment, of type 1 diabetes for at least one year and using insulin for at least 1 year and an insulin pump for at least 6 months
- Criteria for documented hyperglycemia (at least 1 must be met):
 - i. Fasting glucose ≥126 mg/dL
 - ii. Two-hour OGTT glucose ≥200 mg/dL
 - iii. HbA1c ≥6.5% documented
 - iv. Random glucose ≥200 mg/dL with symptoms
 - v. No data at diagnosis is available but the participant has a convincing history of hyperglycemia consistent with diabetes
- Criteria for requiring insulin at diagnosis (1 must be met):
 - i. Participant required insulin at diagnosis and continually thereafter
 - ii. Participant did not start insulin at diagnosis but upon investigator review likely needed insulin (significant hyperglycemia that did not respond to oral agents) and did require insulin eventually and used continually
 - Participant did not start insulin at diagnosis but continued to be hyperglycemic, had positive islet cell antibodies – consistent with latent autoimmune diabetes in adults (LADA) and did require insulin eventually and used continually
- Age ≥18 and <70
- For females, not currently known to be pregnant; If female and sexually active, must agree to use a form of contraception to prevent pregnancy while a participant in the study. A negative pregnancy test will be required for all premenopausal women who are not surgically sterile. Subjects who become pregnant will be discontinued from the study.
- Demonstration of proper mental status and cognition for the study
- Currently using an insulin-to-carbohydrate ratio to calculate meal bolus sizes
- Access to internet and/or cell phone service at home and work
- Ability to access the Internet and upload study data.
- An understanding of and willingness to follow the protocol and sign the informed consent

• Willingness to switch to lispro (Humalog) or aspart (Novolog) if using glulisine (Apidra).

2.2.2 Exclusion

The presence of any of the following is an exclusion for the study:

- Admission for diabetic ketoacidosis in the 12 months prior to enrollment
- Severe hypoglycemia resulting in seizure or loss of consciousness in the 12 months prior to enrollment
- History of a seizure disorder (except hypoglycemic seizure), unless written clearance is received from a neurologist and not currently on a seizure medication
- Cystic fibrosis
- Coronary artery disease or heart failure, unless written clearance is received from a cardiologist or primary care provider
- Pregnancy, breast-feeding, or intention of becoming pregnant over time of study procedures
- A known medical condition that in the judgment of the investigator might interfere with the completion of the protocol such as the following examples:
 - Inpatient psychiatric treatment in the past 6 months
 - Presence of a known adrenal disorder
 - Abnormal liver function test results (Transaminase >2 times the upper limit of normal); testing required for subjects taking medications known to affect liver function or with diseases known to affect liver function
 - Abnormal renal function test results (calculated GFR <60 mL/min/1.73m2); testing required for subjects with diabetes duration of greater than 5 years post onset of puberty
 - Active gastroparesis
 - If on antihypertensive, thyroid, anti-depressant or lipid lowering medication, lack of stability on the medication for the past month (except thyroid medication requires 2 months) prior to enrollment in the study
 - Uncontrolled thyroid disease (TSH undetectable or >10 mlU/L); testing required within 6 months prior to admission for subjects with a goiter, positive antibodies, or who are on thyroid hormone replacement, and within one year otherwise
 - Abuse of alcohol or recreational drugs
 - Infectious process not anticipated to resolve prior to study procedures (e.g. meningitis, pneumonia, osteomyelitis).
 - Uncontrolled arterial hypertension (Resting diastolic blood pressure >90 mmHg and/or systolic blood pressure >160 mmHg).
 - o Oral steroids
 - Uncontrolled microvascular complications such as current active proliferative diabetic retinopathy defined as proliferative retinopathy requiring treatment (e.g. laser therapy) in the past 12 months.
 - A recent injury to body or limb, muscular disorder, use of any medication, any carcinogenic disease, or other significant medical disorder if that injury, medication or

disease in the judgment of the investigator will affect the completion of the protocol

- Basal Rates <0.1 units/hour or minimal total daily basal rates <2.40 units/day.
- Use of the following drugs and supplements during the study:
 - o Acetaminophen
 - Medications being taken to lower blood glucose, such as Pramlintide, Metformin, GLP-1 Analogs such as Liraglutide, and SGLT-2 inhibitors intended to lower blood glucose. Subjects who are on these agents either intermittently or continuously prior to the trial or at the time of screening will be asked to consult with their personal care provider prior to determining whether they can discontinue these agents.
 - Beta-blockers or nutraceuticals intended to lower blood glucose may not be initiated during the trial. Subjects who are on beta-blockers or nutraceuticals intended to lower blood glucose at the time of enrollment may continue on those medications/supplements if the doses have been stable for ≥ 6 months.
 - Any other medication that the investigator believes is a contraindication to the subject's participation

2.3 Informed Consent, Eligibility Assessment and Baseline Data Collection

The study will be discussed with the subject. The subject will be provided with the Informed Consent Form to read and will be given the opportunity to ask questions. If the subject agrees to participate, the Informed Consent Form will be signed. A copy of the consent form will be provided to the subject and another copy will be added to the subject's chart.

Written informed consent must be obtained from the subject prior to performing any studyspecific procedures that are not part of the subject's routine care.

Subjects will be evaluated for study eligibility through the elicitation of a medical history, documentation of a physical examination (by study personnel or local MD) and local laboratory testing if needed to screen for exclusionary medical conditions. Subject exclusion will be at the discretion of the investigator based on study inclusion/exclusion criteria and lab results.

2.3.1 Historical Information and Physical Exam

A history will be elicited from the subject and extracted from available medical records with regard to the subject's diabetes history, current diabetes management, other past and current medical problems, past and current medications, and drug allergies. A standard physical exam (including vital signs and height and weight measurements) will be either performed by the study investigator/ designee (study staff) or a physical exam from the subject's personal physician within 6 months will be reviewed.

2.3.2 HbA1c

HbA1c level will be measured at baseline using the method utilized by the clinic as part of patient care: DCA2000 or equivalent NGSP-certified point-of-care method or local laboratory. HbA1c measurements performed within 4 weeks of randomization may be used.

Chapter 3 STUDY PROTOCOL

3.1 Visit 1 – Screening

At the Screening Visit, the following procedures will be performed / criteria will be checked and documented:

Eligibility Screening Events (to be completed prior to randomization):

- Signed and dated informed consent
- HbA1c assessment via blood draw or fingerstick and DCA2000 or equivalent NGSP-certified point-of-care method (value -4 weeks prior to randomization acceptable)
- Inclusion and exclusion criteria
- Demographics (date of birth, gender, race and ethnicity)
- Diabetic history
- Medical history
- Substance use history (drinking, smoking, and drug habits)
- Concomitant medications
- Physical examination (by study staff or subject's personal MD within 6 mos.)Urine or serum pregnancy test for all premenopausal women who are not surgically sterile
- Blood draw for:
 - Chemistry panel for subjects with diabetes duration of greater than 5 years post onset of puberty (values within 6 months prior to enrollment acceptable).
 - Liver function tests in subjects taking medications known to affect liver function or diseases known to affect liver function (values within 6 months prior to enrollment acceptable).
 - TSH within 6 months for subject with a goiter, positive antibodies, or who are on thyroid hormone replacement. A normal TSH within the past year is otherwise acceptable.
 - \circ Hematocrit

Non-Eligibility Screening Events:

- Weight, height (by study staff or subject's personal MD within 3 mos.)
- Blood pressure and heart rate (by study staff or subject's personal MD within 1 mo.)
- Questionnaires (may be completed electronically):
 - o inControl Technology Expectations Questionnaire (administered prior to starting inControl)
 - inControl Technology Acceptance Questionnaire (administered at subsequent time points after starting inControl)
 - DSPQ_Diabetes Specific Personality Questionnaire (administered at onset of trial only)
 - Clarke Hypoglycemia Awareness Questionnaire
 - DDS_Diabetes Distress Scale
 - High Blood Sugar Survey
 - HFS-II (Part 1 and 2) (Adult Low Blood Sugar Survey)
- All blood glucose meters used in the study (either personal or study provided glucometers) will be QC tested with at least two different concentrations of control solution if available at the start of the study. A tested meter will not be used in a study if it does not read within the

target range at each concentration per manufacturer labeling. The subject will be instructed to perform quality control testing of the BG meter at home per manufacturing guidelines, and to contact study staff for a replacement of the meter, test strips, and control solution if a meter fails the testing.

- Subjects will be asked to perform SMBG measurements at least 4 times daily (before meals, and at bedtime) throughout the study. Subjects will be reminded to use the same glucometer for all finger sticks and calibrations and to only use SMBG values (not CGM values) to guide treatment decisions. Subjects will use their personal glucometer throughout the study but will be provided with a study glucometer if needed.
- Subjects will be provided with a study blood ketone meter and test strips. All study blood ketone meters will be QC tested at the start of the study with at least two different concentrations of control solution if available. A tested meter will not be used in a study if it does not read within the target range at each concentration per manufacturer labeling.
- Subjects will be asked to obtain a glucagon kit per usual care guidelines from their personal physician. If subject is unable to obtain, study physicians may provide a prescription for the subject to obtain at their local pharmacy.

The total amount of blood to be withdrawn during this screening visit is ~9 cc. The visit will last approximately 2-4 hours.

3.1.1 Pilot Study

Prior to implementation of inControl use at home, we will conduct a pilot study of up to 4 subjects using inControl under supervision. This may occur within this protocol or another protocol/IDE (G150221). These subjects will have an approximately 48 hour visit to a research house/hotel. These subjects will be under closed loop control with continuous remote monitoring. We will have a technician and medical personnel (e.g. nurse, EMT) with the subjects at all time. The data will be reviewed by the DSMB and, if no serious adverse events and approved by the DSMB, subjects will continue to be enrolled as described in this protocol.

3.2 Randomization

A subject who meets all the inclusion and exclusion criteria will be enrolled in the study. After completion of the eligibility criteria, the participant will be randomized to one of the two arms: Group A and Group B as described and illustrated in Figure 1.

Subjects who are randomized to Group A will start SAP within four weeks of completing Visit 2; Visit 3 and Visit 4 will occur following completion of SAP.

Subjects who are randomized to Group B will proceed directly to Visit 2, Visit 3 and 4.

All training and run-in visits were structured to accommodate subjects who are experienced with the system or system components as well as subjects who have little to no experience with the system or system components. As a result, training/run-in visits may be combined as described in the protocol depending on the skill level of the individual subject.

3.3 Visit 2 – CGM Training and Run-In

Visit 2 may occur concurrently with Visit 1.

- A urine pregnancy tests may need to be repeated in premenopausal women who are not surgically sterile if Visit 2 occurs more than 6 weeks after their Visit 1.
- Current CGM use will be evaluated, data may be downloaded for any CGM currently in use.
- Eligible subjects will receive study CGM training including proper insertion, calibration and maintenance of the CGM sensor. Training will be tailored to their individual experiences.
- Subjects will take one of three paths forward in the study based on prior CGM experience:
 - **Dexcom CGM users with use in the past 12 weeks** These subjects will not require any further CGM run-in.
 - $\circ~$ Non-Dexcom CGM users (current or past users) or Dexcom CGM users with last use more than 12 weeks prior

These subjects will be given study CGM supplies and move into an up to 1-week home use period with the study CGM to confirm the ability to use the CGM successfully. Subjects may skip this CGM run-in period if subject demonstrates adequate CGM skills.

o CGM non-users

These subjects will be given study CGM supplies and move into an up to 2-week home use period with the study CGM to confirm the ability to use the CGM successfully and to help establish baseline glycemic control during frequent CGM use. Subjects will be contacted weekly by study staff to review CGM use.

- If the subject has not demonstrated adherence to use of CGM after any applicable run-in period, study staff may discontinue that subject at their discretion.
- Subjects will be required to set the CGM hypoglycemia threshold alarm to a value no less than 60 mg/dl and the CGM hyperglycemia threshold alarm to a value no greater than 300 mg/dl.

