The subject must be able to complete system-related tasks independently to be eligible to continue in the study.

3.6 Visit 5 - AP System Run-In phase: Home Use in Pump Only (Open Loop) Configuration

Eligible subjects who have not had recent use of the system (more than ~2 weeks of use in the past 6 months or more than ~2 months of use in the past year) will complete up to 2-week home use period with the full system in pump only (open loop) configuration where no closed loop algorithms are activated. Subject will be instructed not to start closed loop during this run-in phase. Subjects who have had prior experience with the AP system as defined above will not be required to do Visit 5. Subjects who are demonstrating proficiency, as determined by the study physician, may have a shorter open loop run-in phase with a minimum of 5 days duration Criteria for proficiency is listed in section 3.11.

For the inControl system, remote monitoring will be available during this period for the purposes of data collection and ad hoc assessment of system performance by study team. The study team will be available for the subject to contact during this phase. Study staff will contact the subject and review data on the Remote Monitoring once daily. The subject may contact the study staff at any time.

For the Tandem-G6 system, remote monitoring will not be available. Study staff will contact the subject daily to assess difficulties with the use of the system. The subject may contact the study staff at any time. If the study team requires additional information, the subject may be asked to upload the pump at home so that the study can review data on the t:connect website.

3.7 Visit 6 + Visit 7 + Visit 8 Washout Following Completion of the Each Study Phase

At the completion of the each phase of the study, subjects will have up to a two week washout prior to proceeding to the next phase.

First Phase: Group A 8 weeks of SAP; Group B 8 weeks of USS +SAP(d) Second Phase: Group A 8 weeks of USS +SAP(d); Group B 8 weeks of USS + CLC(d) Third Phase: Group A 8 weeks of USS + CLC(d); Group B 8 weeks of USS +SAP (d) Fourth Phase: Group A 8 weeks of USS + SAP(d); Group B 8 weeks of SAP

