6.1 Analysis Plan

Statistical Analysis: The overall analysis will follow Intention-to-treat approach and will use Generalized Linear Mixed Models (e.g. those available in IBM SPSS) including fixed factors following the factorial designs presented in study figure for the specific aims listed below, and random effects reflecting patients' attrition rate.

Metrics:

- (i) Five HbA1c determinations approximately 10 weeks apart;
- (ii) Eight-week sequences of CGM data accompanied by BG self-monitoring readings and recording of the timing of events such as meals and exercise through the GUI
- (iii) Psychometric questionnaires administered concurrently with HbA1c, and
- (iv) Individual structured interview and qualitative/quantitative technology acceptance assessments. CGM data will be used to compute established metrics of risk for hypoglycemia, e.g. the Low BG Index (LBGI), glucose variability, and BG dynamics, as presented in our review of statistical tools for CGM data analysis.

Primary Hypothesis by Specific Aims of the Study

Specific Aim 1: Overnight CLC achieved by USS+SAP(d) will be superior to SAP alone in terms of: (1) Improved HbA1c without increasing the risk for hypoglycemia; (2) Reduced incidence and risk for hypoglycemia overnight, and (3) Reduced fear of hypoglycemia and improved diabetes quality of life scores.

Specific Aim 2: CLC during the day achieved by USS+CLC(d) will preserve the benefits of USS+SAP(d) and will be superior to USS+SAP(d) in terms of: (1) Increased time within target range of 70-180mg/dl during the day; (2) Reduced risk for hypoglycemia during and after exercise, and (3) Reduced postprandial glucose variability.

Specific Aim 3: CLC system acceptance evaluated by an individual structured and technology acceptance scores will be: (1) Superior, for USS+SAP(d) compared to SAP alone, i.e. adding USS overnight will increase patients' acceptance of CLC, and (2) Marginally inferior, for USS+CLC(d) compared to USS+SAP(d); i.e. some patients would prefer SAP alone during the day due to perceived increased system complexity.

Primary Outcomes

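### Randomisation comes before the CGM run-in, so discretionary run-in removals become avoidable post-randomisation losses; the exposure is in the between-sequence and attrition analyses, not the main within-subject contrasts

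*Combined protocol and SAP*

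**What the plan says.** **Order of events.** Section 3.1 heads its list "Eligibility Screening Events (to be completed prior to randomization"; the list contains no CGM run-in or adherence item. Section 3.2 then states: "After completion of the eligibility criteria, the participant will be randomized to one of the two arms". The next steps follow allocation and differ by group. For Group B: "Subjects who are randomized to Group B will proceed directly to Visit 2, Visit 3 and 4". For Group A: "Subjects who are randomized to Group A will start SAP within four weeks of completing Visit 2", with Visits 3 and 4 only after SAP is finished. Section 3.3 allows some flexibility: "Visit 2 may occur concurrently with Visit 1".

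**Removal after the run-in.** Under Section 3.3, if a subject has not shown adherence to CGM after whatever run-in applies, "study staff may discontinue that subject at their discretion". Dexcom users within the past 12 weeks need no run-in. Other current or past CGM users have up to one week, which may be skipped if they show adequate skill. Non-users have up to two weeks.

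**Second condition.** Section 3.5 ends the closed-loop training visit with: "The subject must be able to complete system-related tasks independently to be eligible to continue in the study".

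**Analysis.** Section 6.1 says: "The overall analysis will follow Intention-to-treat approach". It plans random effects for attrition and, under Aim 3, says the attrition effect will inform the reading of system acceptance. No section defines the intention-to-treat set or says how subjects removed before the first phase are followed or analysed.

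**The concern.** A run-in that tests whether people can use the CGM is normally completed before allocation, so that those who cannot are never randomised. Here, in the flow described, it follows allocation. Staff can be inferred to know the sequence, because the next visits differ by group and no masking is described. Removal rests on their judgement, without a threshold.

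Four things are at stake:

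- Subjects removed at this step leave no on-treatment data, so an all-randomised analysis has only their baseline values.
- Section 2.1 aims to balance age and gender and to match baseline HbA1c through randomisation. Later removals can undo this.
- Section 6.1 treats attrition as a signal of acceptance. Removal by staff is a different event from withdrawal by a patient, and the plan does not separate them.
- The losses use up an allowance meant for a study of 44-50 weeks.

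The Visit 4 condition adds an asymmetry. In Group B it is met before any study phase; in Group A it is met after eight weeks of SAP. A person who would fail it contributes SAP data if allocated to A and no phase data if allocated to B.

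**Working it through.** **1. The plan's own figure.** Inputs from Section 6.2: f = 0.2, α = 0.01, power 90%, correlation ρ = 0.4, attrition 31%, 76 completers, 110 randomised. The numbers of groups k and measurements m are not stated; I infer k = 2 and m = 4 from the design. Within-subject repeated-measures F test:

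- λ = f²·N·m/(1 − ρ) = 0.04 × 76 × 4/0.6 = 20.27
- df1 = m − 1 = 3; df2 = (N − k)(m − 1) = 74 × 3 = 222
- critical F at α = 0.01 is 3.87; power = 0.909

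N = 74 gives 0.899, so 76 is the smallest even N that reaches 90%. For attrition, 76/0.69 = 110.1. The stated figures reproduce.

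**2. Effect of run-in losses on numbers.** The documents give no loss rate; 3%, 5% and 10% are assumptions.

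*Losses inside the 31%.* Section 6.2 counts attrition from subjects randomised at baseline, so this is the natural reading. The 76 completers and power of 0.91 stand, but less attrition can be tolerated later:

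| Run-in loss | Left of 110 | Later attrition that still leaves 76 |
|---|---|---|
| 0% | 110 | 1 − 76/110 = 30.9% |
| 3% | 106.7 | 1 − 76/106.7 = 28.8% |
| 5% | 104.5 | 1 − 76/104.5 = 27.3% |
| 10% | 99 | 1 − 76/99 = 23.2% |

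*Losses on top of the 31%.* Apply 0.69 to those left:

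| Run-in loss | Completers | Power |
|---|---|---|
| 3% | 106.7 × 0.69 = 73.6, about 74 | 0.90 |
| 5% | 104.5 × 0.69 = 72.1, about 72 | 0.89 |
| 10% | 99 × 0.69 = 68.3, about 68 | 0.86 |

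**3. Which comparisons are exposed.** Illustrative simulation, all values assumed: two modalities in two orders, subject SD 1, residual SD 0.8, treatment effect 0.3, period effect 0.1, and the lowest 10% of subjects removed from Group B only.

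| Estimate | No removal | After removal |
|---|---|---|
| Within-subject, no treatment-by-subject interaction | 0.298 | 0.298 |
| Within-subject, interaction 0.2 | 0.296 | 0.316 |
| First-period between-group, no interaction | 0.292 | 0.486 |

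One-sided removal hardly moves the cross-over contrast but distorts the between-group comparison. It overstates the case for Visit 2, whose rule is the same in both groups. It is closer to what happens to first-phase data at Visit 4. The within-subject rows use only subjects with both modalities. A mixed model would also give some weight to SAP-only records from Group A, which I have not sized.

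**4. Whether the run-in can move.** Visit 2 is common to both groups, precedes the first phase in both, lasts at most two weeks and may already take place at Visit 1. Section 1.5.2 describes participants as starting with it. Sections 2.3.2 and 3.1 accept an HbA1c from the four weeks before randomisation. Section 3.3, however, foresees Visit 2 more than six weeks after Visit 1, so some screening values would be too old.

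**The case against.** A reader might infer three stronger conclusions. The documents support none of them.

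- **That intention-to-treat cannot be honoured.** Section 6.1 commits to it, and nothing bars keeping discontinued subjects in the analysis set. What is missing is a definition of the set and a rule for follow-up.
- **That the primary treatment comparisons are biased.** Aims 1 and 2 compare modalities that every subject is scheduled to receive, so a subject removed at Visit 2 contributes to neither side. The CGM rule is conditional on non-adherence, exempts recent Dexcom users and is worded identically for both groups. Use of the rule according to allocation is conjecture.
- **That power is lost.** Attrition is counted from randomisation, so the 31% may already cover these losses.

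It can also be said that Visit 2 may coincide with screening, so for some subjects part of the run-in may precede allocation. That is true, but it is permitted, not required, and it makes the order vary between subjects.

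The best remaining argument is that the asymmetric condition is at Visit 4, which cannot sensibly move, and that keeping and following all randomised subjects would deal with both visits. This stands for Visit 4. For Visit 2, retention in the set does not create on-treatment data, whereas randomising later avoids the loss altogether. Visit 3 adds nothing to the concern: Section 3.4 describes pump training but no rule for removing subjects.

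**Conclusion.** The point holds in limited form and is worth an amendment. As described, the plan creates avoidable post-randomisation losses at a step that both groups share before their first phase. These affect mainly the between-sequence Aim 3 comparison, the attrition analysis and the completer count. The Aim 1 and Aim 2 contrasts are little affected: in the illustration the within-subject estimate moved by 0.02 at most (0.296 to 0.316).

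Power is about 0.91 with 76 completers if the losses fall inside the 31%, and about 0.90-0.86 with about 74-68 completers if an assumed 3-10% come on top. This rests on k = 2 and m = 4, on assumed loss rates, and on the inference that staff know the sequence.

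**What to change.** For subjects not yet randomised:

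1. Complete Visit 2 and any applicable CGM run-in before allocation, and randomise only those who pass. Staff judgement at that point cannot depend on the sequence.
2. Leave Visit 4 where it is. Define the intention-to-treat set as all randomised subjects, and collect follow-up on anyone discontinued at Visit 4.
3. In the attrition analysis, code discontinuation by staff separately from withdrawal by the patient.

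Items 2 and 3 should also cover subjects already randomised, as far as their data allow.

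Cost: an amendment that moves one step; allocation up to about two weeks later; and a repeat HbA1c where the screening value falls outside the four-week window. The ceiling of 110 should be counted at randomisation, as Section 6.2 does, so a few more people may need to be screened.
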